### **8.3.5 Week 64 ( $\pm 7$ days relative to Baseline), Week 84, Week 108, Week 132 Visits ( $\pm 14$ days relative to Baseline)**

The subject's dosing interval will change from bimekizumab 320mg Q4W to bimekizumab 320mg Q8W as follows:

- At Week 64 if the subject has not completed the Week 64 visit prior to implementation of Protocol Amendment #5.1.
- At Week 84 if the subject has already completed the Week 72 visit prior to implementation of Protocol Amendment #5.1.
- At Week 108 if the subject has already completed the Week 96 visit prior to implementation of Protocol Amendment #5.1.
- At Week 132 if the subject has already completed the Week 120 visit prior to implementation of Protocol Amendment #5.1.

Subjects whose dosing interval is being changed to bimekizumab 320mg Q8W will receive kits for home administration as follows:

- Subjects whose dosing interval is being changed to bimekizumab 320mg Q8W at Week 64 should be dosed at this visit, and will receive kits for home administration 8 weeks later (Table 7-2).

- Subjects whose dosing interval is being changed to bimekizumab 320mg Q8W at Week 84, Week 108, or Week 132 should NOT be dosed at that visit, and will receive kits for home administration 4 weeks later (Table 7–2).

The following procedures/assessments will be performed/recorded. If IMP is administered on site during this visit, they need to be performed/recorded prior to administration of IMP:

- Physical exam including evaluation of signs and symptoms of active TB and risk for exposure to TB
- Vital signs (sitting systolic and diastolic BP, pulse rate, and body temperature) should be obtained prior to blood sampling
- Collection of blood and urine samples for the following tests should be obtained prior to dosing:
  - Hematology and biochemistry
  - Urinalysis
  - Urine pregnancy test
- Tuberculosis questionnaire
- PASI
- Percentage of BSA
- IGA
- Patient symptoms (itch, pain, and scaling)
- PHQ-9
- eC-SSRS
- Concomitant medication
- AEs
- Contact IRT

After completion of the above-mentioned procedures, administration of IMP will occur:

- At each of these visits for subjects on bimekizumab 320mg Q4W dosing, preferably by self-injection under supervision of the site personnel. This only applies to those subjects who have not yet changed to Q8W after implementation of Protocol Amendment #5.1.
- At Week 64 only for those subjects on bimekizumab 320mg Q8W dosing, preferably by self-injection under supervision of the site personnel.

Distribution of IMP and accountability activities for home administration to be performed as described in Section 7.2, Section 7.5, and Section 7.7. Home pregnancy tests will be provided for testing every 4 weeks as appropriate (Table 5–2).

### **8.3.6 Week 72 ( $\pm 7$ days relative to Baseline) and Week 120 Visits ( $\pm 14$ days relative to Baseline)**

The subject's dosing interval will change from bimekizumab 320mg Q4W to bimekizumab 320mg Q8W as follows:

- At Week 72 if the subject has already completed the Week 64 visit prior to implementation of Protocol Amendment #5.1.
- At Week 120 if the subject has already completed the Week 108 visit prior to implementation of Protocol Amendment #5.1.

As depicted in Table 7–2, subjects whose dosing interval is being changed to bimekizumab 320mg Q8W at one of these visits should be dosed at this visit and will receive kits for home administration 8 weeks later.

The following procedures/assessments will be performed/recorded prior to administration of IMP:

- Physical exam including evaluation of signs and symptoms of active TB and risk for exposure to TB
- Vital signs (sitting systolic and diastolic BP, pulse rate, and body temperature) should be obtained prior to blood sampling
- Collection of blood and urine samples for the following tests should be obtained prior to dosing:
  - Hematology and biochemistry
  - Urinalysis
  - Urine pregnancy test
  - Bimekizumab plasma concentrations
  - Anti-bimekizumab antibodies
- Tuberculosis questionnaire
- PASI
- Percentage of BSA
- IGA
- DLQI
- Patient symptoms (itch, pain, and scaling)
- PHQ-9
- scalp IGA for subjects with scalp involvement at Baseline
- mNAPSI for subjects with nail involvement at Baseline
- pp-IGA for subjects with palmoplantar involvement at Baseline
- EQ-5D-3L

- 
- eC-SSRS
  - Concomitant medication
  - AEs
  - Contact IRT
  - After completion of the above-mentioned procedures, administration of IMP will occur, preferably by self-injection under supervision of the site personnel.

Distribution of IMP and accountability activities for home administration to be performed as described in Section 7.2, Section 7.5, and Section 7.7. Home pregnancy tests will be provided for testing every 4 weeks as appropriate (Table 5–2).

### 8.3.7 Week 96 Visit ( $\pm 14$ days relative to Baseline)

The subject's dosing interval will change from bimekizumab 320mg Q4W to bimekizumab 320mg Q8W at Week 96 if the subject has already completed the Week 84 visit prior to implementation of Protocol Amendment #5.1. As depicted in Table 7–2, subjects whose dosing interval is being changed to bimekizumab 320mg Q8W at Week 96 should be dosed at this visit, and will receive kits for home administration 8 weeks later.

The following procedures/assessments will be performed/recorded prior to administration of IMP:

- Physical exam including evaluation of signs and symptoms of active TB and risk for exposure to TB
- Body weight
- Vital signs (sitting systolic and diastolic BP, pulse rate, and body temperature) should be obtained prior to blood sampling
- Collection of blood and urine samples for the following tests should be obtained prior to dosing:
  - Hematology and biochemistry
  - Urinalysis
  - Urine pregnancy test
  - IGRA tuberculosis test
  - Bimekizumab plasma concentrations
  - Anti-bimekizumab antibodies
- Record 12-lead ECG
- Tuberculosis questionnaire
- PASI
- Percentage of BSA
- IGA

- 
- DLQI
  - Patient symptoms (itch, pain, and scaling)
  - PHQ-9
  - scalp IGA for subjects with scalp involvement at Baseline
  - mNAPSI for subjects with nail involvement at Baseline
  - pp-IGA for subjects with palmoplantar involvement at Baseline
  - PASE
  - PGADA (only for subjects with PsA)
  - WPAI-SHP V2.0
  - EQ-5D-3L
  - eC-SSRS
  - Concomitant medication
  - AEs
  - Contact IRT

At Week 96, after completion of the above-mentioned procedures, administration of IMP will occur, preferably by self-injection under supervision of the site personnel

Distribution of IMP and accountability activities for home administration to be performed as described in Section 7.2, Section 7.5, and Section 7.7. Home pregnancy tests will be provided for testing every 4 weeks as appropriate (Table 5-2).

### **8.3.8 Week 144 Visit ( $\pm 14$ days relative to Baseline)**

The following procedures/assessments will be performed/recorded prior to administration of IMP:

- Physical exam including evaluation of signs and symptoms of active TB and risk for exposure to TB
- Body weight
- Vital signs (sitting systolic and diastolic BP, pulse rate, and body temperature) should be obtained prior to blood sampling
- Collection of blood and urine samples for the following tests should be obtained prior to dosing:
  - Hematology and biochemistry
  - Urinalysis
  - Urine pregnancy test
  - IGRA tuberculosis test
  - Bimekizumab plasma concentrations

---

– Anti-bimekizumab antibodies

- Record 12-lead ECG
- Tuberculosis questionnaire
- PASI
- Percentage of BSA
- IGA
- DLQI
- Patient symptoms (itch, pain, and scaling)
- PHQ-9
- scalp IGA for subjects with scalp involvement at Baseline
- mNAPSI for subjects with nail involvement at Baseline
- pp-IGA for subjects with palmoplantar involvement at Baseline
- PASE
- PGADA (only for subjects with PsA)
- WPAI-SHP V2.0
- EQ-5D-3L
- eC-SSRS
- Concomitant medication
- AEs
- Contact IRT

Return of IMP and accountability activities for home administration to be performed as described in Section 7.2, Section 7.5, and Section 7.7.

If Protocol Amendment #5.4 is implemented at the time subjects are treated in the OLE Period (ie, up to Week 144; OLE2 Group A subjects), these subjects will be invited to participate in the OLE2 Period and may directly roll over and continue their treatment from the Week 144/OLE2 Baseline Visit as long as they do not meet any of the withdrawal criteria and have provided informed consent.

If Protocol Amendment #5.4 is implemented at the time subjects have completed the Week 144 Visit and are in the SFU Period of the OLE Period or have completed the SFU of the OLE Period (Group B subjects), these subjects will be invited to enter the OLE2 Period to reinitiate their treatment in the OLE2 Period. However, before receiving the first dose at the Week 144/OLE2 Baseline Visit, they will first undergo screening during the 4-week OLE2 Screening Period (Section 8.4.1).

## **8.4 OLE2 Period**

### **8.4.1 OLE2 Screening (up to 4 weeks) – applicable for OLE2 Group B only**

Prior to any study specific activities of the OLE2 Period, subjects who completed the Week 144 Visit and are in the SFU or have completed the SFU of the OLE Period (OLE2 Group B subjects) will undergo screening. Subjects who have used systemic treatments after Week 144 must have stopped this treatment 1 month prior to receiving the first bimekizumab injection in the OLE2 Period. Screening procedures may be performed during this time. Subjects receiving systemic immunomodulatory medications for an indication other than PSO must have their eligibility confirmed by the Medical Monitor prior to enrollment in the OLE2 Period.

At the Screening Visit of the OLE2 Period (OLE2 Screening Visit), subjects will be asked to read, sign, and date an ICF that has been approved by the Sponsor and an IRB/IEC and that complies with regulatory requirements. Subjects will be given adequate time to consider any information concerning the study given to them by the Investigator or designee. As part of the informed consent procedure, subjects will be given the opportunity to ask the Investigator any questions regarding potential risks and benefits of continued participation in the study.

The following procedures/assessments will be performed at the OLE2 Screening Visit for subjects in the OLE2 Group B:

- Informed consent
- Inclusion/exclusion
- Urine drug screen
- Significant past medical history including clinically relevant past or coexisting medical conditions and surgeries (only applicable for subjects who completed the SFU, only new or modified medical history since completing the SFU should be entered in eCRF)
- AEs (only for subjects in the SFU)
- Physical exam
- Vital signs (sitting systolic and diastolic BP, pulse rate, and body temperature) should be obtained prior to blood sampling
- Collection of blood and urine samples for the following clinical laboratory tests:
  - Hematology and biochemistry
  - Urinalysis
  - Urine pregnancy test
  - Hepatitis B and Hepatitis C
  - HIV
- Tuberculosis questionnaire
- PASI
- Percentage of BSA

- 
- IGA
  - PHQ-9
  - eC-SSRS
  - Prior and concomitant medication (including new or modified medications initiated after SFU)
  - Contact IRT

#### **8.4.2 OLE2 Baseline Visit**

Subjects who will still be treated in the OLE Period at the time of implementing Protocol Amendment #5.4 (OLE2 Group A subjects) will attend Week 144 Visit and directly roll over to the OLE2 Period to continue their treatment (bimekizumab 320mg Q8W). They will undergo all study assessments of the Week 144 Visit and will receive bimekizumab 320mg Q8W at this visit, which will also coincide with the first visit of the OLE2 Period, ie, the Week 144/OLE2 Baseline Visit.

Subjects who have completed Week 144 Visit and are in the SFU of the OLE or have completed the SFU Period at the time of Protocol Amendment #5.4 implementation (OLE2 Group B subjects) will reinitiate their treatment at the Week 144/OLE2 Baseline Visit, and will be assigned a treatment regimen based on their disease severity at the Week 144/OLE2 Baseline Visit (bimekizumab 320mg Q4W/Q8W for subjects with IGA score  $\geq 3$  or bimekizumab 320mg Q8W for subjects with IGA score  $< 3$ ).

##### ***Applicable for OLE2 Groups A and B:***

- Physical exam
- Body weight
- Vital signs (sitting systolic and diastolic BP, pulse rate, and body temperature) should be obtained prior to blood sampling
- Collection of blood and urine samples for the following clinical laboratory tests:
  - Hematology and biochemistry
  - Urinalysis
  - Urine pregnancy test
- eC-SSRS
- Tuberculosis questionnaire
- PASI
- Percentage of BSA
- IGA
- PHQ-9
- DLQI

- Patient symptoms (itch, pain, and scaling)
- Concomitant medication
- AEs
- Contact IRT

***Additional Procedures/assessments applicable for OLE2 Group A***

- Informed Consent
- ECG
- Blood sample for bimekizumab plasma concentrations
- Blood sample for anti-bimekizumab antibodies
- IGRA TB test
- scalp IGA
- mNAPSI
- pp-IGA
- EQ-5D-3L
- PASE
- PGADA
- WPAI-SHP V2.0

At the Week 144/OLE2 Baseline Visit, after completion of the above-mentioned procedures, administration of IMP will occur, preferably by self-injection under supervision of the site personnel.

Distribution of IMP and accountability activities for home administration to be performed as described in Section 7.2, Section 7.5, and Section 7.7.

**8.4.3 Self-injection at home (OLE2 Weeks 4, 8, 16, 32, and 40)**

Subjects receiving bimekizumab 320mg Q8W will be given the opportunity for self-injection of bimekizumab at home on the following weeks: OLE2 Weeks 8, 16, 32, and 40.

Subjects receiving bimekizumab 320mg Q4W/Q8W will be given the opportunity for self-injection of bimekizumab at home on the following weeks: OLE2 Weeks 4, 8, and 16. At OLE2 Week 16, subjects receiving bimekizumab 320mg Q4W/Q8W will switch to bimekizumab 320mg Q8W regimen and will be given the opportunity for self-injection of bimekizumab at home dosed at OLE2 Weeks 32 and 40.

Subjects of childbearing potential should conduct a home pregnancy test every 4 weeks. In case of a scheduled home self-injection the pregnancy test needs to be performed immediately prior to self-injecting bimekizumab at home. If the pregnancy test result is positive, IMP should not be administered and the site should be contacted.

Adverse events will be captured spontaneously if the subject decides to visit the site to receive the bimekizumab administration.

All used syringes will be disposed of by subjects/caregivers as determined by the Investigator in an acceptable disposal (sharps) container directly after the administration. The subjects/caregivers return the documentation together with any used/unused containers at the next scheduled clinic visit.

#### **8.4.4 OLE2 Week 12, Week 24, and Week 36 Visits ( $\pm 14$ days relative to OLE2 Baseline)**

As depicted in Table 7-3, subjects receiving bimekizumab 320mg Q4W/Q8W should receive IMP at the OLE2 Week 12 Visit, and all subjects will receive kits for home administration 4 weeks later at OLE2 Week 16. All subjects will receive IMP administration at the OLE2 Week 24 Visit, and will receive kits for home administration 8 weeks later. At the OLE2 Week 36 Visit, subjects will not be dosed and will receive kits for home administration 4 weeks later at OLE2 Week 40.

The following procedures/assessments will be performed/recorded at every clinic visit prior to administration of IMP:

- Physical exam
- Vital signs (sitting systolic and diastolic BP, pulse rate, and body temperature) should be obtained prior to blood sampling
- Urine pregnancy test, for applicable subjects
- Tuberculosis questionnaire
- PASI
- Percentage of BSA
- IGA
- Patient symptoms (itch, pain, and scaling)
- PHQ-9
- eC-SSRS
- Concomitant medication
- AEs
- Contact IRT

The following will be additional assessments will be performed / recorded every 24 weeks (ie, OLE2 Weeks 24 and 48) prior to administration of IMP

- Collection of blood and urine samples for the following tests should be obtained prior to dosing:
  - Hematology and biochemistry

- 
- Urinalysis
  - DLQI

At the OLE2 Week 12 and Week 24 Visit, after completion of the above-mentioned procedures, administration of IMP will occur, preferably by self-injection under supervision of the site personnel.

Distribution of IMP and accountability activities for home administration to be performed as described in Section 7.2, Section 7.5, and Section 7.7. Home pregnancy tests will be provided for testing every 4 weeks as appropriate (Table 5-2 and Table 5-3).

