#### 5.2.4 OLE2 Period

Subjects enrolled as per Protocol Amendment #5.1 will be treated in the OLE Period until Week 136 (last dose of bimekizumab 320mg Q8W) and will be followed in a SFU Period for 20 weeks after attending the Week 144 Visit (see Section 5.2.3). After the implementation of Protocol Amendment #5.4 (addition of a 48-week treatment period, ie, OLE2 Period), subjects will be invited to continue or reinstate their treatment as per the following OLE2 Groups:

- OLE2 Group A: Subjects in the treatment phase of the OLE Period at the time of Protocol Amendment #5.4 implementation will attend the Week 144 Visit and directly roll over to the OLE2 Period. These subjects will continue receiving bimekizumab 320mg Q8W for 40 additional weeks, starting from the first treatment visit of the OLE2 Period (ie, Week 144/OLE2 Baseline Visit; the Week 144 Visit will coincide with the Week 144/OLE2 Baseline Visit and data collected at this visit will be used as baseline data for subjects entering the OLE2 Period).
- OLE2 Group B: Eligible subjects who have completed the Week 144 Visit and are in the SFU or have completed the SFU of the OLE Period at the time of Protocol Amendment #5.4 implementation, will reinstate their treatment in the OLE2 Period after having undergone Screening assessments during a 4-week OLE2 Screening Period. The first dose will be administered at the Week 144/OLE2 Baseline Visit and data collected at this visit will be used as baseline data for the OLE2 Period. Subjects in OLE2 Group B with an IGA score  $\geq 3$  at the Week 144/OLE2 Baseline Visit will be treated with bimekizumab Q4W for the first 16 weeks, and then will switch to bimekizumab 320mg Q8W. Subjects in OLE2 Group B with an IGA score  $< 3$  at the Week 144/OLE2 Baseline Visit will be treated with bimekizumab Q8W from the Week 144/OLE2 Baseline Visit.

During the OLE2 Period (Week 144/OLE2 Baseline to OLE2 Week 48), all subjects will attend study visits every 12 weeks. All subjects will be treated until OLE2 Week 40 (last dose of bimekizumab 320mg Q8W).

Following completion or early withdrawal from the OLE2 Period, subjects will undergo the SFU of the OLE2 Period (SFU2) and will return for the SFU2 Visit 20 weeks after the last dose of IMP administration.

The assessments to be performed at each visit of the OLE2 Period are presented in [Table 5-3](#).

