**Table 5-3: Schedule of study assessments, OLE2 Period**

| Visit a/
Week | OLE2 Period                 |                       |         |         |          |          |          |          |          |          | OLE2 Groups A + B |                  |
|-----------------------------|-----------------------------|-----------------------|---------|---------|----------|----------|----------|----------|----------|----------|-------------------|------------------|
|                             | OLE2 Screening b | W144/OLE2
Baseline | OLE2 W4 | OLE2 W8 | OLE2 W12 | OLE2 W16 | OLE2 W24 | OLE2 W32 | OLE2 W36 | OLE2 W40 |                   | OLE2W48/
PEOT |
|                             | C                           | C                     | H       | H       | C        | H        | C        | H        | C        | H        | C                 | C                |
| Protocol activity    |                             |                       |         |         |          |          |          |          |          |          |                   |                  |

l Q4W IMP administration only applies to those subjects who have entered the OLE2 Period as part of Group B, and had an IGA  $\geq 3$  upon entry of OLE2 Period. These subjects will receive Q4W dosing for 16 weeks, then will change from Q4W to Q8W dosing. Subjects who have entered the OLE2 Period as part of Group B with an IGA  $< 3$  upon entry of OLE2 Period will receive Q8W dosing from the W144/OLE2 Screening Visit onwards.

m The dosing window is  $\pm 14$  days relative to the Week 144/OLE2 Baseline Visit.

[figure not shown]
n If self-injected at home, the subject/caregiver will document the date, body location, kit number and time point of administration of study medication. All used syringes will be disposed of by subjects/caregivers as determined by the Investigator in an acceptable disposal (sharps) container directly after the administration. The subjects/caregivers return the documentation together with any used/unused containers at the next scheduled clinic visit.

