### 6.4.2 OLE2 Period Group A subjects

To participate in the OLE2 Period, subjects still treated in the OLE Period and who completed the Week 144 Visit by the time of the implementation of Protocol Amendment #5.4 will not need to fulfil other eligibility criteria than those listed in Section 6.4.1 and will continue their treatment from the Week 144/OLE2 Baseline Visit if they do not meet any of the withdrawal criteria defined in Section 6.5.

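### Two extension-period dosing instructions contradict other protocol text (OLE2 Week 12 for Q8W subjects, Week 72 after a Week 64 switch), and two lesser wording faults need correcting with them

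*Protocol*

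**What the plan says.** **OLE2 Week 12.** The first paragraph of Section 8.4.4 states that "subjects receiving bimekizumab 320mg Q4W/Q8W should receive IMP at the OLE2 Week 12 Visit". It has every subject dosed at Week 24 and none at Week 36. After the list of assessments the section returns to dosing: "At the OLE2 Week 12 and Week 24 Visit, after completion of the above-mentioned procedures, administration of IMP will occur". No regimen is named there. Section 8.4.3 has Q8W subjects injecting "at home on the following weeks: OLE2 Weeks 8, 16, 32, and 40".

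**Week 64 to Week 72.** Section 8.3.5 says that subjects whose interval changes to Q8W "at Week 64 should be dosed at this visit, and will receive kits for home administration 8 weeks later". Table 7-2 footnote b repeats this. Section 5.2.3 counts Week 72 among the clinic visits, and Section 8.3.6 says of that visit: "After completion of the above-mentioned procedures, administration of IMP will occur, preferably by self-injection under supervision of the site personnel". Week 72 is not on the Q8W home list in Section 8.3.4 or on the general home list in Section 7.7.

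**Start of Group B dosing.** Under Table 5-3 footnote l, Group B subjects with IGA below 3 "will receive Q8W dosing from the W144/OLE2 Screening Visit onwards". Section 5.2.4 says "The first dose will be administered at the Week 144/OLE2 Baseline Visit". Sections 7.2 and 8.4.2 agree with 5.2.4, and footnote m of the same table counts its dosing window from the OLE2 Baseline Visit.

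**Definition of Group A.** Section 6.4.2 describes subjects who are still on OLE treatment and "who completed the Week 144 Visit by the time of the implementation of Protocol Amendment #5.4 will not need to fulfil other eligibility criteria" beyond the common ones in Section 6.4.1. Sections 5.2.4, 5.2.5 and 8.3.8 give direct rollover to subjects who have yet to attend Week 144, and place those past it, in or after safety follow-up, in Group B.

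**The concern.** Section 8 is the text that sites work from visit by visit. At OLE2 Week 12 the same section gives two answers for a Q8W subject, and the unrestricted one stands where staff reach the dosing step. At Week 64 the site is told to dispense a home kit for a week in which the subject is also due in clinic for a supervised dose.

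What is at stake is subject safety first, then the extension data. Section 5.8.1 gives long-term safety, including safety after a treatment interruption, as a purpose of OLE2. Section 14.3.2.2 summarises OLE2 efficacy by treatment group. If some Q8W subjects received an extra dose, the regimen label would no longer describe what they received. If Group A has two definitions, so does the split between continued and re-started treatment.

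**Working it through.** The inputs are the visit weeks, home lists and footnotes of Sections 5.2.3, 5.2.4, 7.7, 8.3.4 to 8.3.6, 8.4.3, 8.4.4 and Table 7-2. The dose cells of Tables 5-3, 7-2 and 7-3 are not legible in the extracted text, so only prose and footnotes are used.

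**1. Reproduce the OLE2 home lists.** The Q8W grid is 0 + 8k for k = 0 to 5: Weeks 0, 8, 16, 24, 32, 40, which is 6 doses. The clinic visits are Weeks 0, 12, 24, 36, 48. Removing them leaves 8, 16, 32, 40, exactly the list in 8.4.3. The Q4W/Q8W schedule is 0, 4, 8, 12, 16, 24, 32, 40. Removing the clinic visits leaves 4, 8, 16, 32, 40, again as 8.4.3 states. The calendar is therefore consistent, and Week 12 belongs to the second schedule only.

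**2. Apply the closing sentence of 8.4.4 to Q8W.** The doses become 0, 8, 12, 16, 24, 32, 40: 6 + 1 = 7 occasions, with intervals of 8, 4, 4, 8, 8 and 8 weeks. Comparable visits in the first extension do limit the dosing step by regimen (8.3.2 for Week 52; 8.3.5 for Weeks 64, 84, 108 and 132), so the missing limit here departs from the protocol's own pattern.

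**3. Reproduce the OLE home list.** The Q8W grid from Week 48 is 48, 56, 64, 72, 80, 88, 96, 104, 112, 120, 128, 136. Removing the clinic visits (48, 52, 56, 64, 72, 84, 96, 108, 120, 132) leaves 80, 88, 104, 112, 128, 136, as in 8.3.4.

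**4. Check each switch visit.** Week for the kit = switch week + offset, with the offset from Table 7-2 footnotes b (8 weeks) and c (4 weeks):

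| Switch visit | Offset | Kit for Week | Kind of week |
|---|---|---|---|
| 64 | 8 | 72 | clinic visit, dosing on site |
| 72 | 8 | 80 | home |
| 84 | 4 | 88 | home |
| 96 | 8 | 104 | home |
| 108 | 4 | 112 | home |
| 120 | 8 | 128 | home |
| 132 | 4 | 136 | home |

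Six of seven land on a listed home week; only Week 64 does not. If both instructions were followed, the outer limit is 2 × 320mg = 640mg around Week 72. The home pregnancy-test list in Section 12.3.2 also omits Week 72.

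**5. Footnote l.** The visit label that it uses combines W144 with Screening. The column heading of Table 5-3 attaches W144 to Baseline, Section 8.4.1 lists no IMP administration at OLE2 Screening, and Section 8.4.2 assigns the regimen from the IGA at Baseline.

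**6. Section 6.4.2.** The last Q8W dose in the OLE is at Week 136 and Week 144 is the end-of-treatment visit (5.2.3). A subject past Week 144 is therefore not ordinarily still on OLE treatment. Taken together, the two conditions in 6.4.2 describe almost nobody, and they do not match Group A as defined elsewhere.

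**The case against.** The best defence is that other text and systems would catch these errors. The opening of 8.4.4 names the regimen dosed at Week 12, and the IRT, which is contacted at each of these visits, assigns kits by visit schedule (7.10). Section 7.2 limits take-home syringes to those needed for home doses. Home administration forms come back at the next clinic visit for investigator review (7.2, 7.7). That stands as far as it goes: a seventh dose or 640mg is a worst case and not an expected outcome. It does not remove the conflict. An IRT follows whichever instruction was programmed, and the protocol does not say which one that is.

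A reader might infer more, and the documents do not support it:

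- That 6.4.2 lets Group B subjects in without re-entry screening. It does not on its words: it also requires that the subject is still on OLE treatment, and 6.4.3 separately applies its criteria to everyone in or past safety follow-up.
- That footnote l starts dosing up to 4 weeks before Baseline. The surrounding text, including footnote m, points to a slip in the visit name.
- That subjects could be re-dosed with no pregnancy, suicidality or laboratory checks. Both groups have a urine pregnancy test, eC-SSRS, PHQ-9 and laboratory sampling at OLE2 Baseline ahead of IMP (8.4.2). Hepatitis and HIV testing and the urine drug screen are done only at Group B screening.

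**Conclusion.** The concern holds for two dosing instructions. At OLE2 Week 12, Section 8.4.4 contradicts itself and 8.4.3, with 7 dosing occasions against 6 for Q8W subjects on a literal reading. At Week 72, Section 8.3.5 and Table 7-2 footnote b contradict 5.2.3, 8.3.6, 8.3.4 and 7.7, for one switch visit in seven. Footnote l and Section 6.4.2 are lesser wording faults to be corrected at the same time.

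Every conflict falls after the Week 48 assessments, so the primary Week 16 analysis and the Week 48 comparisons are unaffected. The effect is on subject safety and on OLE and OLE2 exposure data. This rests on the prose and footnotes alone. The protocol does not show how the IRT was programmed or how many subjects switched at Week 64, so no frequency of error can be given.

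**What to change.** The sponsor must reconcile:

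- the two statements in 8.4.4 with each other, with 8.4.3 and with Table 7-3;
- 8.3.5 and Table 7-2 footnote b with 5.2.3, 8.3.4, 8.3.6 and 7.7 for Week 72;
- Table 5-3 footnote l with 5.2.4, 7.2, 8.4.2 and footnote m;
- 6.4.2 with 5.2.4, 5.2.5 and 8.3.8.

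The result should be one instruction for each regimen and visit, and one definition of Group A. Sites should be notified, and doses already given at OLE2 Week 12 and at Week 72 checked against the assigned regimen. No dose or entry rule is proposed here; that choice is the sponsor's. The cost is a clarification letter or minor amendment and a check of dosing records, with no statistical cost.
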